4.7.2 MBS Recorded After IP is Taken

Subjects that record their MBS after taking the investigational product (IP) are considered failures for the analysis of MBS.

4.7.3 Primary Efficacy Endpoints

In addition to the analyses described below, data regarding the co-primary efficacy endpoints, pain freedom and freedom from MBS at 2 hours post-dose will be presented in a by-subject listing that includes treatment group, historical MBS, MBS at time of onset of study migraine, initial migraine severity, gender, presence or absence of aura, and use of prophylactic migraine medication.

4.7.3.1 Pain Freedom at 2 Hours Post-Dose

Pain freedom is assessed using the number of mITT subjects that report pain levels of “none” at 2 hours post-dose on a 4-point Likert scale (0=none, 1=mild, 2=moderate, 3=severe). The information from the 4-point scale is directly summarized as follows:

A table showing descriptive statistics for the observed data, which includes the number and percentage of subjects reporting each of the 4 pain levels at 2 hours post-dose, and the percentage of subjects with missing data, for each treatment group. The table will include exact (Clopper-Pearson) 95% CIs for each percentage. This table will be repeated for Asian subjects only.

The estimand for the primary analysis is the percentage of pain free subjects. In statistical terms, this percentage is arrived at by estimating the probability or the “risk” that a subject is pain free.

The population summary, the between group difference in the percentage of pain free subjects is assessed by computing the “risk difference” between treatment groups. This is evaluated by computing the common risk difference, using Cochran-Mantel-Haenszel (CMH) weights (sample size weights), stratified by the use of prophylactic migraine medication (yes or no). The risk difference is tested at a two-sided alpha level of 0.05. Missing data at 2 hours post-dose will be imputed as failures (NC=F). If a stratum (prophylactic medication use: yes or no) has sparse data (less than 5 subjects), then the strata will be pooled.

Results presented for the primary analysis include the following:

- The number and percentage of subjects who are pain free, and those not pain free, at 2 hours post-dose. These are presented by stratum and treatment group, with asymptotic standard errors (ASE), and 95% asymptotic CIs.
- Common risk difference with sample size, p-value, ASE, and 95% asymptotic CIs.
- Risk difference within each stratum with sample size, p-value, ASE, and 95% asymptotic CIs.

- A forest plot of the risk differences within each stratum, and common risk difference (similar to the risk difference plot produced by SAS Proc Freq).
- Common risk for each treatment with sample size, ASE, and 95% asymptotic CIs.

The primary analysis will be repeated for the subgroups described in [Section 4.2.6](#).

Sensitivity analyses will be conducted as follows:

1. The primary analysis is repeated, using the mITT population, with missing data at 2 hours post-dose imputed using Last Observation Carried Forward (LOCF). Baseline Observation Carried Forward (BOCF) is permitted.
2. The primary analysis is repeated using only data from complete cases (data present at baseline and 2 hours).
3. The primary analysis is executed using the mITT population, and multiple imputation (with 20 imputations; $m=20$) methods to impute missing data at 2 hours post-dose using the copy from reference approach. The fully conditional specification (FCS) method is used with a generalized logit distribution. Covariates may include use of prophylactic medication (yes or no), sex, migraine intensity at onset (severe or other), migraines per month ($<$ median, \geq median), and the subject's MBS at time of study migraine onset (nausea, photophobia, or phonophobia).
4. A series of "what if" analyses are conducted that show what the analysis results would look like if the missing data in each treatment group were replaced with data from subjects having success rates that vary over the range of 0, 10, 20 and 30 percent. The results of this analysis are presented in a 4x4 matrix, with the rows representing the success rates for the placebo group and the columns representing the success rates for the BHV-3000 group. For example, the "30,0" cell shows the hypothetical result when a responder rate of 30% replaces the missing placebo data, and a responder rate of 0% replaces the missing BHV-3000 data. Each cell in this table will show the common risk difference, asymptotic 95% CI and uncorrected p-value. The table will be accompanied by a forest plot that displays the 16 CIs.

4.7.3.2 *Freedom from MBS at 2 Hours Post-Dose*

Freedom from each subject's MBS is assessed using the number of mITT subjects who report that their MBS (reported at migraine onset) is absent at 2 hours post-dose. The symptoms that can be nominated as the MBS (phonophobia, photophobia or nausea) are measured using a binary scale (0=absent, 1=present).

Subjects who reported their MBS after taking IP, or who did not provide an MBS are considered failures in this analysis.

Tabulations will be presented as follows:

The number and percentage of subjects reporting each of the migraine associated symptoms (phonophobia, photophobia or nausea) by treatment group and overall as most bothersome, subjects with a missing MBS, and subjects who reported their MBS after taking study medication.

An overall cross tabulation of the historical MBS (reported at screening) as rows, and the MBS reported at the onset of the treated migraine as columns. This tabulation only includes subjects with both assessments. P-value from a chi-square test will be reported along with the values and confidence limits for both Asymmetric Lambda and Symmetric Lambda.

The estimand, difference in percentage of MBS free subjects (“risk difference”) between treatment groups, is evaluated by computing the common risk difference, using CMH weights (sample size weights), stratified by the use of prophylactic migraine medication (yes or no). The risk difference will be tested at a two-sided alpha level of 0.05. Missing data at 2 hours post-dose will be imputed as failure (NC=F). Also, the use of rescue medication prior to providing data at the 2 hour assessment, taking IP prior to reporting the MBS, or failure to report a MBS are events that are imputed as treatment failures. If a stratum (prophylactic medication use: yes or no) has sparse data (less than 5 subjects) then the strata will be pooled.

The results to be presented for the primary analysis of MBS include those described in items (a) through (e) for the primary analysis of pain freedom ([Section 4.7.3.1](#)). In this case, the “risk” is now the probability of being MBS free at two-hours post-dose.

The primary analysis of MBS will be repeated for the subgroups described in [Section 4.2.6](#).

Sensitivity analyses will be conducted as follows:

1. The primary analysis is repeated, using the mITT population, with missing data at 2 hours post-dose imputed using LOCF. BOCF is permitted.
2. The primary analysis is repeated, using only data from complete cases (data present at baseline and 2 hours).
3. The primary analysis is executed using the mITT analysis set, and multiple imputation (with 20 imputations; $m=20$) methods to impute missing data at 2 hours post-dose using the copy from reference approach. The FCS method is used with a generalized logit distribution. Covariates may include use of prophylactic medication (yes or no), sex, migraine intensity at onset (severe or other), migraines per month ($<$ median, \geq median), and the subject’s MBS at time of study migraine onset (nausea, photophobia, or phonophobia).
4. A matrix of “what if” analyses, similar to that created for the co-primary endpoint of pain freedom, is created for freedom from the MBS.
5. The primary analysis will be repeated, using the mITT population, with the addition of a stratum that reflects the subject’s self-reported MBS at the time of study migraine onset (nausea, phonophobia, or photophobia).

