4.2.6 Subpopulations

The subgroups of interest for this study:

Age: Categorized as < 40 , ≥ 40 years

Race: white, black or African American, other (including Asian) , Asian only. Certain tables may be created for the Asian population only; but in the subgroup analyses, Asian subjects will generally be included in the “other” category due to low counts.

Sex: Female/Male

Aura: Presence/Absence

Headaches per Month: Categorized as $< \text{median}$, $\geq \text{median}$, where median is calculated overall across treatment groups combined for mITT subjects.

Triptan Non-Responder: Yes/No

Cardiovascular (CV) Risk Contraindicating Triptans: Yes/No

Subgroup analyses will be performed for the primary efficacy endpoints only.

Triptan non-responders are identified using the “Prior Triptan Response” Case Report Form (CRF) pages, which capture reasons for discontinuing triptans taken historically. The definition of triptan non-responder is based on the number of triptans that a subject failed for efficacy reasons. For each triptan and route of administration, the subject is asked the questions shown in Table 5. A subject is considered to have failed a drug for efficacy reasons if they indicated “most or all of the time” for any of the reasons in the table.

A triptan non-responder is defined as any subject that fails two or more molecular entities for efficacy reasons. To be considered a failure for a molecular entity, the subject must have failed on all routes of administration that the subject tried for the molecular entity.

Table 5: Questions Used to Determine Triptan Non-response

	Most or All of the Time	Some of the Time	Rarely	Never
The treatment took too long to relieve my headache pain.				
The pain returned after it was relieved within 24 hours				
The treatment did not relieve my other symptoms (nausea, sensitivity to light or sound, for example).				
I could not count on this treatment to relieve my pain and symptoms every time				

Subjects with CV risk that contraindicates triptans are identified using the “Cardiac and Other Risk Factors” CRF pages. The pages are used to identify subjects with cardiovascular conditions cited in triptan labels as contraindications. A subject is identified as someone with cardiovascular risk factors contraindicating triptans if any of the following questions are answered as “yes”:

Does the subject have ischemic coronary artery disease?

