4.7.4.1 Freedom from Photophobia, Phonophobia or Nausea at 2 Hours

Freedom from photophobia, phonophobia, and nausea are assessed, by treatment group, by tabulating the number of mITT subjects who reported the presence of the symptom at migraine onset who then report the absence of the symptom at 2 hours post-dose. Subjects who report the symptom at baseline, but have missing data at 2 hours post-dose will be imputed as failures (NC=F). Also, subjects in the analysis set that take rescue medications on or before providing their 2 hours post-dose data are imputed as failures.

The principal measurement for the associated symptoms (phonophobia, photophobia, and nausea) is made on a binary scale (0 = absent; 1 = present). An exploratory measurement of these symptoms was also made on a 4 point Likert scale (0=none, 1=mild, 2=moderate, 3=severe).

For these three endpoints, the difference between treatment groups is evaluated by computing the common risk difference, using CMH weights (sample size weights), stratified by the use of prophylactic migraine medication (yes or no). The risk difference is tested at a two-sided alpha level of 0.05. If a stratum (prophylactic medication use: yes or no) has sparse data (less than 5 subjects) then the strata are pooled.

The results presented for the analysis of each symptom include those described in items (a) through (e) for the primary analysis of pain freedom ([Section 4.7.3.1](#)). In this case, the “risk” is the probability of being free from the symptom of interest at 2 hours post-dose. In addition, the following display will be created for each of the 3 symptoms:

A table showing descriptive statistics for the 4-point scale, which includes the number and percentage of subjects reporting each of the 4 symptom levels at 2 hours post-dose, and the percentage of subjects with missing data, for each treatment group. The table will include exact (Clopper-Pearson) 95% CIs for each percentage.

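### In sparse prophylaxis-by-subgroup cells, the planned asymptotic 95% intervals for the co-primary endpoints can cover well below 95% and can have zero width; this affects descriptive output only

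*SAP*

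**What the plan says.** SAP 4.7.3.1 lists the outputs for pain freedom at 2 hours. For the counts and percentages of responders: "These are presented by stratum and treatment group, with asymptotic standard errors (ASE), and 95% asymptotic CIs". For the treatment comparison: "Risk difference within each stratum with sample size, p-value, ASE, and 95% asymptotic CIs". Alongside these come the common risk difference, a forest plot of the stratum and common differences, and the common risk for each arm. On testing: "The risk difference is tested at a two-sided alpha level of 0.05".

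The sparse-data rule is: "If a stratum (prophylactic medication use: yes or no) has sparse data (less than 5 subjects), then the strata will be pooled". SAP 4.7.3.2 carries the same rule and outputs over to freedom from the most bothersome symptom (MBS), and 4.7.4.1 repeats the rule ("has sparse data (less than 5 subjects) then the strata are pooled"). None of these sections, nor 4.2.3 on pooling, says whether the 5 is counted over both arms or in each.

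On subgroups, 4.7.3.1 says: "The primary analysis will be repeated for the subgroups described in" Section 4.2.6, and 4.7.3.2 does the same for MBS. Section 4.2.6 restricts subgroup analyses to the primary endpoints. Its list includes "Cardiovascular (CV) Risk Contraindicating Triptans: Yes/No".

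Exact Clopper-Pearson intervals are planned for the observed four-level pain table and its Asian-only repeat. No score or exact interval, continuity correction or minimum cell size is given for the stratum and subgroup risk differences. The SAP does not use the name Wald, but an asymptotic interval built from an asymptotic standard error (ASE), with SAS Proc Freq as the model for the plot, is that interval.

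**The concern.** The Wald interval estimates its own standard error from the observed proportions. With a handful of subjects per arm, those proportions are often 0 or 1, and the standard error collapses. If each arm has no responders or all responders, the estimated standard error is exactly 0 and the interval is a single point labelled as a 95% interval.

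Repeating the primary analysis in each subgroup splits that subgroup again by prophylaxis, which is where very small cells are most likely. A threshold of 5 subjects leaves many cells in which the approximation fails. At stake is false precision in the smallest groups. These may include the subgroup with cardiovascular contraindications to triptans, which the protocol rationale treats as an area of unmet need.

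**Working it through.** **Inputs from the documents.** Nominal level 95%, so z = 1.96. Allocation 1:1. Phase 2b pain-freedom rates 31.4% vs 15.3% (Protocol 1.2.2.8), the only 2-hour pain-freedom rates given. Pooling below 5 subjects. About 600 treated per arm.

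**Assumed inputs.** The rates 20% vs 12% and 35% vs 27%, and all subgroup and prophylaxis shares. The documents give none of these.

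**The plan's own figure.** 715 × 0.85 = 607.75, which the SAP rounds to about 600 per arm. It reproduces.

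**Coverage of the risk-difference interval.** The interval is d ± 1.96·√(p₁(1−p₁)/n₁ + p₂(1−p₂)/n₂), with observed proportions. Coverage is the sum of the two binomial probabilities over every pair of counts whose interval contains the true difference. With equal arms:

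| Per arm | 31.4% vs 15.3% | 20% vs 12% (assumed) |
|---|---|---|
| 3 | 76% | 56% |
| 5 | 76% | 76% |
| 10 | 92% | 89% |
| 30 | 94% | 94% |
| 600 | 95% | 95% |

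The Newcombe (Wilson-score) interval covers about 93 to 99.9% in small cells at all four rate pairs tried: these two, 35% vs 25%, and 10% vs 5%.

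**Zero width.** The probability is [p₁ⁿ + (1−p₁)ⁿ]·[p₂ⁿ + (1−p₂)ⁿ]. At 3 per arm and 31.4% vs 15.3% this is (0.031 + 0.323) × (0.004 + 0.608) = 0.354 × 0.611 = 0.22. At 20% vs 12% it is 36% at 3 per arm, 17% at 5 and 3% at 10. For comparison, with 0/3 in both arms the Wilson upper limit for each arm is z²/(n + z²) = 3.84/6.84 = 0.56, so the Newcombe interval runs from −56 to +56 points while the Wald interval is a point at 0.

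**The two readings of the pooling rule.** If the 5 is a stratum total, a stratum of exactly 5 is analysed. Averaged over random 1:1 splits with at least one subject per arm, coverage is then 60% at 31.4% vs 15.3% (zero width in 33% of samples) and 47% at 20% vs 12% (46%). If the 5 is per arm, the smallest cell is 5 vs 5, where coverage is still about 76% at both rate pairs in the table.

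**Single-arm intervals by stratum.** For a true rate of 15%, the one-sample Wald interval covers 38% at n = 3, 53% at n = 5, 79% at n = 10 and 90% at n = 15.

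**How small could cells be?** If 2 to 5% of 600 per arm fall in the cardiovascular-risk subgroup, that is 12 to 30 per arm. If 10 to 20% of those use prophylaxis, the stratum holds 12 × 0.10 = 1.2 to 30 × 0.20 = 6 per arm. The lowest part of that range would already be pooled.

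**Where it does not matter.** A full-population prophylaxis stratum of only 5% of 600 is 30 per arm, and coverage is 94% at 31.4/15.3, 20/12 and 35/27. At 60 per arm it is about 95%.

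**Equal true rates.** With 15% in both arms and equal arm sizes, coverage is 92% at 3 per arm, 98% at 5 and 92% at 10. The shortfall therefore arises mainly when there is a real difference.

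**The case against.** The strongest reply is that almost nothing of consequence depends on these intervals. No confirmatory test or gatekeeping step uses them. The sample size is printed beside each within-stratum difference and the counts are given by stratum and arm, so a reader can see that a zero-width interval came from 0/3 vs 0/3. That stands, and it sets the severity.

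Several stronger readings are tempting, but the documents do not support them:

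- A reader might infer that all stratified or secondary results are unreliable. At full-population stratum sizes the interval is adequate, and subgroup analyses are limited to the co-primary endpoints.
- A reader might infer that exclusions 2b and 2c largely empty the cardiovascular-risk subgroup. They remove uncontrolled, unstable or recent disease and uncontrolled hypertension. The SAP definition also counts any past stroke or TIA, peripheral vascular disease, ischemic bowel disease and accessory-pathway arrhythmia, and inclusion 2h admits subjects with triptan contraindications.
- A reader might cite the Asian-only output ("Certain tables may be created for the Asian population only"). The same sentence merges Asian subjects into the other-race category for most subgroup work because counts are low, and the one Asian-only efficacy table listed in Appendix 1 uses exact intervals.
- A reader might infer that the faulty intervals will appear on subgroup forest plots split by stratum. Appendix 1 lists one by-subgroup plot per co-primary endpoint and no stratum-within-subgroup figure.
- A reader might take the 5-subject threshold as a stratum total. The text does not say so.

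What the reply leaves untouched is that the SAP specifies this interval for every stratum that escapes pooling, and that the threshold does not protect it on either reading.

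**Conclusion.** The point holds in a narrow form. For the co-primary endpoints, the interval rule as written can produce intervals labelled 95% that cover roughly 55 to 92% at 3 to 10 per arm when the arms truly differ, and that are sometimes zero-width. This arises mainly in prophylaxis strata inside a rare subgroup. The size depends on the rates. At the documents' own rates the figures are about 76% at 3 to 5 per arm and 92% at 10; the 56% figure rests on the assumed 20% vs 12%. The documents give no subgroup or prophylaxis counts, so such cells are plausible but not shown to occur.

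The common risk difference, its test and full-population strata of about 30 or more per arm are essentially unaffected. With equal rates and equal arm sizes, coverage stays at 92 to 98% for 3 to 10 per arm, so this is not mainly a false-positive problem. Severity is minor: an improvement to descriptive output that the sponsor should consider.

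**What to change.** Keep the common risk difference and its test as they are. In SAP 4.7.3.1 and 4.7.3.2, specify score-type intervals for within-stratum and subgroup displays: Wilson for a single proportion, and Newcombe or Miettinen-Nurminen for a difference. State in each section that carries the sparse-data rule (also 4.7.4.1) that fewer than 5 subjects is counted per arm. Clarifying the count is not enough alone, because 5 per arm still gives about 76% coverage with the present interval.

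The cost is an interval option in the programs and a sentence or two in the SAP. The confirmatory tests do not change. The downside is that small-cell intervals become wider.

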4.7.4 Secondary Efficacy Endpoints

If the co-primary endpoint tests are both significant, then the secondary endpoints are evaluated using a fixed sequence approach, with each test in the hierarchy conducted at $p=0.05$. See [Section 4.2.5](#) for the testing order.

4.7.4.1 Freedom from Photophobia, Phonophobia or Nausea at 2 Hours

Freedom from photophobia, phonophobia, and nausea are assessed, by treatment group, by tabulating the number of mITT subjects who reported the presence of the symptom at migraine onset who then report the absence of the symptom at 2 hours post-dose. Subjects who report the symptom at baseline, but have missing data at 2 hours post-dose will be imputed as failures (NC=F). Also, subjects in the analysis set that take rescue medications on or before providing their 2 hours post-dose data are imputed as failures.

The principal measurement for the associated symptoms (phonophobia, photophobia, and nausea) is made on a binary scale (0 = absent; 1 = present). An exploratory measurement of these symptoms was also made on a 4 point Likert scale (0=none, 1=mild, 2=moderate, 3=severe).

For these three endpoints, the difference between treatment groups is evaluated by computing the common risk difference, using CMH weights (sample size weights), stratified by the use of prophylactic migraine medication (yes or no). The risk difference is tested at a two-sided alpha level of 0.05. If a stratum (prophylactic medication use: yes or no) has sparse data (less than 5 subjects) then the strata are pooled.

The results presented for the analysis of each symptom include those described in items (a) through (e) for the primary analysis of pain freedom ([Section 4.7.3.1](#)). In this case, the “risk” is the probability of being free from the symptom of interest at 2 hours post-dose. In addition, the following display will be created for each of the 3 symptoms:

A table showing descriptive statistics for the 4-point scale, which includes the number and percentage of subjects reporting each of the 4 symptom levels at 2 hours post-dose, and the percentage of subjects with missing data, for each treatment group. The table will include exact (Clopper-Pearson) 95% CIs for each percentage.

4.7.4.2 Pain Relief (at 60 Minutes; at 90 Minutes; at 2 Hours)

Pain relief at the specified timepoint post-dose is assessed by tabulating the number of mITT subjects that report a pain level of none or mild (responses of 0 or 1 on the 4-point Likert scale) at the specified timepoint post-dose, by treatment group. Subjects with missing data at the specified timepoint post-dose will be imputed as failures (NC=F).

The results to be presented for the analysis include those described in items (a) through (e) for the primary analysis of pain freedom ([Section 4.7.3.1](#)). In this case, the “risk” is the probability of pain relief at the specified timepoint post-dose.

4.7.4.3 *Probability of Requiring Rescue Medication within 24 Hours*

Whether or not a subject took rescue medication within 24 hours after the initial dose of study medication is tabulated by treatment group using mITT subjects, and the percentages are compared between treatment groups.

The results are presented for the analysis include those described in items (a) through (e) for the primary analysis of pain freedom ([Section 4.7.3.1](#)). In this case, the “risk” is the probability of not requiring rescue medication within 24 hours post-dose.

Information regarding the rescue medication, including the type, date and time taken, dose, route and form of administration, and frequency, is presented in a listing by subject and treatment group.

4.7.4.4 *Functional Disability Scale (at 60 Minutes; at 90 Minutes; at 2 Hours)*

Impact of treatment on subject disability is assessed using a single-question, FDS. Subjects rate the level of disability they perceive as a result of their migraine in performing normal actions using a 4-point scale: Normal Function, Mild Impairment, Severe Impairment, or Required Bedrest. The proportion of mITT subjects who have a response of “normal” at the specified timepoint post dose will be evaluated as the endpoint of interest.

The information from the 4-point scale will be directly summarized as follows:

A table showing descriptive statistics for the 4-point scale, which includes the number and percentage of subjects reporting each of the 4 disability levels at the specified timepoint post-dose, and the percentage of subjects with missing data, for each treatment group, using the observed data. The table will include exact (Clopper-Pearson) 95% CIs for each percentage.

The results to be presented for the analysis include those described in items (a) through (e) for the primary analysis of pain freedom ([Section 4.7.3.1](#)). In this case, the “risk” is now the probability of a functional disability level of “normal” at the specified timepoint post-dose.

4.7.4.5 *Sustained Pain Freedom from 2 to 24 Hours*

Sustained pain freedom is assessed using the number of mITT subjects that experienced no headache pain (response of 0 on Likert scale) at all time points from 2 through 24 hours post-dose. Subjects with missing pain scores at 1 or fewer time points, given that they have responses of no pain (response of 0 on 4-point Likert scale) at all other time points including the 2 and 24 hour post-dose time points, will be considered as successes. Subjects with responses missing at greater than 1 post-dose time point, missing data at the 2 or 24 hour time point, or with any pain score greater than 0 will be considered as failures.

The results to be presented for the analysis include those described in items (a) through (e) for the primary analysis of pain freedom ([Section 4.7.3.1](#)). In this case, the “risk” is the probability of sustained pain freedom from 2 to 24 hours.

